Participants will be trained on the different behavioral tasks that they will be performing during the MRI scanner: the face perception task and the social games. There will be specific instructions and a practice session on the computer screen for each of these tasks. Participants will complete a quiz for the face perception task and for the ball-game to double check the comprehension of the task. If there are errors in responses, the experimenter will repeat the instructions or, if necessary, present some training sessions on the screen and repeat the questions that participants did not answer correctly, until he has all the answers correct.

At the end of this visit, participants will go through a brief clinical standardized interview (Bio-behavioral clinical global interview BB-CGI) with the experimenter during which the experimenter will ask questions to the subject and record their interactions.

This clinical test will be repeated at the end of each of the following 4 MRI visits in order to evaluate the progress or come up with a score of socio-emotional, verbal, physiological and clinical index of improvement.

We will take a photo from this video to keep the photo identification in the folder of the patient.

At the end of the interview, the study staff will take the patient to the BITC MRI scanner at the Emory Hospital for a practice/habituation session. The participant will lay down in the scanner (same way as described below during the clinical visits), get familiarized with the coil and the tunnel, with the response box (that he will use to answer during games), with the noise, and to with some examples of the tasks that he will perform during the actual clinical visits. We will run an fMRI sequence for few minutes (that might include a resting state, face test, ball-game). At the end of the MRI training/habituation, we will ask participants few questions about his experience. The participant will be also asked about any adverse events. In case of mild anxiety, the experimenter will make sure to give the participant time to rest and ask him if he would like to continue habituation.

Participants will also have a look at the CRN unit.

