- **Blood draw:** 5 minutes after spray intake, a registered nurse from the CRN will collect 10 ml of blood by venipuncture for subsequent baseline measurement of plasma oxytocin. Blood will be collected in a lavender-top EDTA-treated tube. Samples will be immediately centrifuged at 4C by the CRN core laboratory and the plasma and blood cells will be stored at -80 until assay.
- **Vital signs:** 15 minutes after spray intake, temperature, heart rate and blood pressure will be re-evaluated by the CRN nurse to check for any side effects of IN-OT. There are several pieces of evidence of safety and absence of side effects from chronic and acute intake of IN-OT. Thus, we do not expect any side effects from the hormone oxytocin intake. However, we will ask subjects if they feel any side effects. If no side effects are reported, but temperature has increased or decreased more than 2 degrees, heart rate is above 100 bpm, or blood pressure is above 140/90, the vitals will be re-measured. If levels remain elevated after 3 successive recordings in both limbs (total of 6 recordings) measured at least 5 minutes apart, the study physician will be notified and asked to advise on how to treat the subject and whether it is safe to continue with the protocol. Subjects may still be included at the discretion of the study physician. If subjects were to experience a serious adverse event, such as a heart attack or an anaphylactic reaction, a code will be called and, if necessary, the subject will be taken to the Emory ER. [name] or/and [name] and the CRN nurses will be notified by the experimenter. [name] or [name] will call to admit the subject to the ER. As we already mentioned, it is not likely that oxytocin has any side effects based on the growing evidence in the literature. In addition to vital signs, we will ask participants if they feel any side effects.

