  - **Face Rating questionnaire (post MRI):** participants are asked to rate (on a scale 1 to 7) faces.
  - **A social learning test (SLT):** participants are asked to match faces and words as fast as they can.
  - **Emotion Matching test (EMT):** participants are asked to identify the emotion that is displayed on a face by matching the emotional face that appears on the left to one of the faces that appears to the right (different faces but same emotion).
  - **Toronto Alexithymia scale:** participants are asked to complete a simple questionnaire.
  - **Mood questionnaire (PANAS scale).**
  - **BB-CGI (clinical interview):** the same interview that is performed during the pre-MRI visit will be performed during this visit in order to collect a clinical score of improvement as well as physiological, verbal and socio-emotional improvements.

4- Second, Third and Fourth visit of scan (ASD subjects) (total duration= around 3 to 4 hours each): The exact same procedures will be performed during these other 3 visits. These 3 additional visits will be conducted only in ASD subjects. Also, participants will receive different content of spray (either different dose of oxytocin or placebo).

Of note, the health assessment will be reviewed one more time (in addition to the assessment during the first pre-clinical visit) by the nurse practitioner or the study physician during one of the 4 clinical visits, if the original health assessment expires (more than 30 days).

	Screening and consent review/training	Vital signs 1	Blood samples Pre	Hormone Spray (PL, 8, 24, 48 IN-OT)	Blood samples post	Vital signs 2	MRI scan	Post MRI scan
Visit 1	X	X	X	X	X	X	Rest+ 3 tasks	Quest+ 2 tasks + clinical interview
Visit 2	X	X	X	X	X	X	Rest+ 3 tasks	Quest+ 2 tasks + clinical interview
Visit 3	X	X	X	X	X	X	Rest+ 3 tasks	Quest+ 2 tasks + clinical interview
Visit 4	X	X	X	X	X	X	Rest+ 3 tasks	Quest+ 2 tasks + clinical interview

Table 2: Clinical trial visits for subjects with ASD

Visits will be separated by a one-week interval approximately ( $\pm$  2 to 3 days). We have to be flexible with the scheduling given that we are facing challenges while scheduling all the units and personals. Every patient will receive the 3 doses of IN-OT (8IU, 24IU, 48IU) and placebo in a double blind, placebo controlled trial.

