**Intranasal OT administration:** With a single dose of Syntocinon, no adverse side effects of the substance are to be expected. To further minimize risk, subjects will receive OXT at Emory Hospital (CRN unit at ACTSI). To monitor potential side effects of OXT administration, temperature, heart rate and blood pressure will be measured before hormone administration and 15 minutes after hormone administration. Experimenter will again ask if the subject is experiencing any of the following symptoms: chest pain, difficulty breathing, itching. If the subject

reports any of these symptoms, the study physician or study nurse practitioner will be contacted and asked to advise on how to treat the subject and whether it is safe to continue with the protocol. If necessary, a code will be called. If no side effects are reported, but temperature has increased or decreased more than 2 degrees, heart rate is above 100 bpm, or blood pressure is above 140/90, the subject will be asked to sit quietly for 10 minutes after which vital signs will be re-measured. If vital signs are within the normal range, and no side effects are reported, they will proceed through the experiment. If not, the study physician or study nurse practitioner will be contacted and asked to advise on how to treat the subject and whether it is safe to continue with the protocol. If subjects were to experience a serious adverse event, such as a heart attack or an anaphylactic reaction, a code med will be called and, if necessary, the subject will be taken to the Emory ER. [name] or [name] and the CRN nurses will be notified by the project coordinator. [name] or [name] will call to admit the subject to the ER.

**Blood Draw:** Subjects will be monitored for signs that they may faint such as clammy skin, dizziness, confusion, irregular breathing, and decreased blood pressure. If these signs are observed, subjects will be asked to lie down with their legs elevated and blood pressure will be monitored until symptoms subside. If a subject loses consciousness and requires medical attention while in the Anthropology Building, Emory First Responders will be contacted (911). If a subject loses consciousness and requires medical attention while at the Biomedical Imaging Technology Center in Emory University Hospital, study staff will instruct the MRI technician to call a hospital code for medical care.

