### **Randomization and blinding**

**Clinical trial for ASD subjects:** The trial will be a double-blind, placebo-controlled, several doses of oxytocin, within subject design study. Patients will undergo 4 clinical visits (in addition to a first pre-clinical visit) during which they receive 12 puffs (6 in each nostril) of 8IU total, 24IU and 48IU oxytocin (syntocinon) and placebo (assigned randomly). The placebo will contain the same ingredients as syntocinon, except the active molecule oxytocin. This is essential for making sure that the patient does not recognize the type of treatment he is receiving. Hence, both patients and the experimenter will be blind to the type of the treatment administered.

The pharmacy IDS of Emory will be in charge of the randomization sequence and one of the staff members of the team (who is not involved in testing procedures) will be de-blinded.

We will break the blind after testing 25 patients with ASD to check the results half-way for a mid-point analysis. The mid-point analysis will focus on measures where effect sizes are anticipated to be large enough that the risk of false positives is minimal. We are expecting larger effect size on some measures and therefore we break the blind for those measures to be analyzed and published. Additional data on these measures will continue to be collected and we will attempt to publish the combined analysis at the end to avoid publication bias.

However, the data collection will continue until a sample size equal to 50. Given that we are facing challenges with ASD recruitment and that the study requires the participation in 5 long visits, it is possible that the study will stop at N=30 or 40, in case the PI was not able to recruit more ASD. We also expect dropouts after recruitment. We believe that we will be able to test 30 patients with ASD.

It is possible that this project will be funded by other grant funds which will allow adding more participants (more 50 ASD). In this case, the PI will submit an amendment accordingly.

**Healthy subjects:** There will be only one clinical visit for healthy subjects and they will all receive placebo spray (12 puffs, 6 per nostril). The study will be conducted in a single-blind design. The PI is aware that the subject is receiving placebo. However, the participant will be told that he might

receive oxytocin or placebo. This is important in order to control for the placebo effect on behavior and brain activity.

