Clinical visits (4 visits): Each participant will participate in 4 clinical visits at the CRN unit at the Emory Hospital and at BTCI MRI scanner. All the rules below apply for healthy subjects and for patients with ASD.

Based on prior literature, we have a list of expected adverse events that could be linked to oxytocin inhalation or placebo inhalation. This list includes any random symptom that was mentioned in trials previously conducted on single administration of oxytocin and placebo. They are considered random because some of them occurred during placebo spray intake, some of them were not found to be significantly different between placebo and oxytocin, and some of them are mentioned in the medical brochure. The list of expected adverse events includes:

- 1- Nausea or mild nausea
- 2- Vomiting or tendencies to vomit
- 3- Headaches
- 4- Irregularities of the pulse (tachycardia, bradycardia, arrhythmia, very rare hypertension)
- 5- Skin rashes and allergic reactions
- 6- Shortage of breath
- 7- Blood pressure decrease
- 8- Circulatory collapse
- 9- Runny nose

- 10- Tiredness
- 11- Sore throat
- 12- Shakiness
- 13- Sweating
- 14- Coughing

Participants will not be given this list and asked explicitly about it. Instead, the experimenter will ask participants how they are feeling following spray administration.

Participants will be also asked upon arrival on the 2nd, 3rd, 4th and 5th visit if there were any changes in their health.

In this clinical trial, we do not expect serious adverse events, and given that the subject is receiving 3 doses and placebo across 4 different visits (within the same study), we would like to define the terminology of reportable events and a plan to notify the IRB of reportable events:

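### No adverse-event contact is scheduled after a participant's last spray, and no symptom question at the dosing visits is tied to the end of the scan or to departure

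*Combined protocol and SAP*

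**What the plan says.** **After departure.** The Data and Safety Monitoring Plan, under the clinical visits, has participants asked on arrival at the second, third, fourth and fifth "visit if there were any changes in their health". Visit 1 is the undosed pre-clinical visit; the four sprays are given at visits 2 to 5 (Table 2, Appendix B). On spacing: "Visits will be separated by a one-week interval approximately", give or take 2 to 3 days.

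**Within a dosing visit.** Adverse events are asked about before the spray. Afterwards, "15 minutes after spray intake, temperature, heart rate and blood pressure will be re-evaluated by the CRN nurse", and at that check: "In addition to vital signs, we will ask participants if they feel any side effects". The risk section places a question on three named symptoms at the same check: "Experimenter will again ask if the subject is experiencing any of the following symptoms: chest pain, difficulty breathing, itching". The safety plan adds that "the experimenter will ask participants how they are feeling following spray administration", with no time given. The resting scan starts at 40 minutes. The itemised post-scan list holds a face rating, two computer tests, the alexithymia and mood scales and the recorded interview.

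**At the undosed visit.** After the habituation scan in the pre-clinical visit, the plan says: "The participant will be also asked about any adverse events".

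**Withdrawal.** Randomization and blinding says: "We also expect dropouts after recruitment". Under Participant selection, a withdrawal leads to a note to file and a report to the IRB at continuing review. The DSMB report is to include the number of dropouts and their reasons, along with safety concerns and adverse events.

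**Healthy subjects.** They receive one placebo spray at a single visit. The group recruited from the general population has an earlier screening visit, so the spray visit is still their last.

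**The concern.** A question asked on arrival can only look back to the previous visit. Whatever comes last is therefore never asked about, and which treatment comes last depends on the randomised order. A patient who stops early has the same gap after the final spray received, and early leavers may include those who tolerated a spray poorly.

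The plan also commits to reporting serious events that occur off site or between visits, whether or not they are judged related. After the last spray, staff would learn of such an event only if the participant volunteered it.

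Within the visit, the symptom check with a fixed time precedes the scan. The plan writes an adverse-event question into the scan visit where no drug is given, but not into the post-scan steps of the visits where it is.

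The issue is whether events are collected, not how they are classified afterwards.

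**Working it through.** The plan gives no figure for safety coverage, so there is none to reproduce. The check maps each spray to the next scheduled question, then counts.

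**Mapping for a completer**

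| Spray | Given at | Next scheduled question about the period since | Recall interval |
|---|---|---|---|
| 1 | visit 2 | arrival at visit 3 | about 4–10 days |
| 2 | visit 3 | arrival at visit 4 | about 4–10 days |
| 3 | visit 4 | arrival at visit 5 | about 4–10 days |
| 4 | visit 5 | none | none |

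The interval is 7 − 3 = 4 to 7 + 3 = 10 days. Arrival at visit 2 precedes any spray, so it collects nothing about treatment.

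**Count.** Inputs: 4 sprays per patient (Table 2); 50 patients planned, possibly stopping at 30 or 40 (Randomization and blinding).

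- N=50: 50 / (4 × 50) = 50/200 = 25%
- N=40: 40/160 = 25%
- N=30: 30/120 = 25%

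If order is balanced (an assumption; the plan says only that assignment is random), three of the four treatments are oxytocin, so the expected number of oxytocin sprays in last place is 0.75 × 50 = 37.5 or 0.75 × 30 = 22.5.

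**Dropout.** Each dosed patient has exactly one uncovered spray: the fourth, or the last before leaving. Dropout therefore leaves the count per patient at one and shrinks the denominator. If a fraction *d* leave after *m* sprays, the uncovered share is 1 / [4(1 − *d*) + *d·m*]. The plan gives no dropout rate, so as an assumed range:

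- *d* = 0.1, *m* = 3: 1 / (3.6 + 0.3) = 25.6%
- *d* = 0.4, *m* = 1: 1 / (2.4 + 0.4) = 35.7%

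**Healthy subjects.** Adding the planned 30, each with one uncovered placebo spray: (50 + 30) / (200 + 30) = 80/230 = 34.8% at N=50, or (30 + 30) / (120 + 30) = 60/150 = 40% at N=30.

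**Within the visit.** The order is: spray; timed check at 15 minutes; scan from 40 minutes; post-scan tasks and interview; departure. The untimed question in the safety plan is satisfied by asking it at 15 minutes. Nothing places it after the scan.

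**The case against.** Several stronger readings are tempting, and the documents do not support them.

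- *Events during or after the scan go unasked.* Too strong. The safety plan's question on how participants feel could be put after the scan, the MRI risk section provides continuous visual and auditory monitoring during scanning, and staff interview patients with ASD afterwards. What stands is that no adverse-event question is tied to the end of the scan or to departure. Logging events after testing is record-keeping, not a question.
- *Dropouts are ignored.* They are not: withdrawals go to the IRB and dropout reasons to the DSMB. What stands is that no safety contact is scheduled to obtain events from those who leave.
- *The 15-minute check misses the plan's own drug-effect window.* The times in the Objectives are when measurements are taken. The plan does not call them a window for effects or harms.
- *Each dropout adds an uncovered spray.* Not per dosed patient, as shown above.
- *Appendix B proves the absence.* It has no adverse-event row at all, even for questions the text requires, so its silence is weak evidence. The point rests on the text sections. Consent pages are not available here and may tell participants how to report problems, but that still relies on volunteering.
- *The comparison between doses is biased.* Random order spreads the gap roughly evenly over treatments, and safety is not an outcome of any aim. Events after departure are also classed as unrelated by rule, so a follow-up contact alone would not change the treatment-related count.

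The strongest objection is timing. The healthy-subject screening section says all patients for the study have been tested, and Amendment 5 refers to the patients' five visits in the past tense. If so, a new contact reaches no further oxytocin spray. Yet Randomization and blinding still describes continuing to 50, with a possible further 50, and healthy recruitment is open. This limits the prospective benefit without removing the gap in the data already collected.

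**Conclusion.** The point holds in this form. Scheduled collection of events after departure covers sprays 1 to 3 and omits one spray per dosed patient with ASD: 25% of sprays among completers, and 25.6% to 35.7% under the assumed dropout range. The healthy subjects' only spray is also omitted. About three quarters of the uncovered ASD sprays are oxytocin if order is balanced. At the dosing visits, the only timed post-spray symptom check comes before the scan.

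The consequence is an adverse-event record that is incomplete and depends on visit order, together with a weaker basis for the plan's own commitment to report off-site serious events. No efficacy analysis is affected. How much can still be corrected depends on whether ASD testing is in fact complete, on which the sections disagree.

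**What to change.** 1. In the Data and Safety Monitoring Plan and Appendix B, ask the existing health-change question once more, by phone or email, after the last spray received. Include patients who withdraw and healthy subjects. The interval is for the sponsor and investigator to set.
2. In the post-scan procedures and Appendix B, place the existing question on how participants feel after the scan and before departure at each dosing visit, and log the answer.
3. Reconcile the statement that ASD testing is complete with the text describing recruitment to 50 and possibly beyond.
4. For patients already tested, state in the safety report that events after departure following the last spray were not actively collected.

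Cost: one short contact per participant through channels already used for screening and scheduling, and about a minute per visit by staff already present. The drawback is one extra contact, which some participants will not answer; non-response should be recorded.

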## **Data and Safety Monitoring Plan**

Pre-clinical visit (visit 1) Participants will perform behavioral tests, fill questionnaires, provide saliva DNA samples and conduct training (see above for more details). The training might occur at the Emory hospital or at the Laboratory of Darwinian Neuroscience (as part of the collaboration with [name], PhD) that is located at the anthropology building at Emory University. Participants with ASD might be able to lay down inside the scanner for training purposes to habituate to the context.

We do not expect any serious adverse event and if any adverse event happened during the first visit. We expect several adverse events:

- 1- Tiredness

2- Moderate anxiety or fear reaction in response to lying down in the MRI scanner for ASD.

Participants will be asked how they feel. However, the PI or the experimenter will make sure to take note of these potential adverse events or any unexpected adverse events. All unexpected adverse events related to the first visit will be reported promptly to the IRB and DSMB. All serious adverse events related or not to the first visit will be reported promptly to the IRB, DSMB and to the sponsor. Serious adverse event (based on FDA documentation) includes: life-threatening adverse event, inpatient hospitalization or prolongation of existing hospitalization, a persistent or significant incapacity or substantial disruption of the ability to conduct a normal life functions, or a congenital anomaly/birth defect). Unexpected adverse event is an adverse event that is not listed in the investigator brochure or is not listed at the specificity or severity that has been observed or is not consistent with the risk information described in the protocol.

Severity grading scale for adverse events will be based on this following chart (FDA-based):

- **Grade 1:** mild: asymptomatic or mild symptom; clinical observations only; no intervention indicated
- **Grade 2:** Moderate: minimal, local or noninvasive intervention indicated, have some effect on daily activity
- **Grade 3:** Severe or medically significant that affects daily activity but not immediately life-threatening; hospitalization or prolongation of hospitalization indicated; disabling.

We do not consider any event as related to the study unless if the participant was on-site at Emory with the experimenter. All events that occurred before participants' arrival and after participants' departure will be considered unrelated.

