**Relatedness:** the PI will consider that any event (serious, unanticipated, death, adverse event, not serious) is related to the treatment only if the event occurred internally during the clinical visit after spray intake (4 clinical visits at CRN unit at Emory Hospital and BITCI MRI scanner at the Emory Hospital). Thus, an event is considered as a related adverse event or a related unanticipated event if it occurred during the few hours of testing (up to 4 hours) and will not be considered related to the treatment once the subject leaves the hospital. The PI will take note of all related expected adverse events (list above) in a log document and report them periodically to the sponsor and the IRB during the continuing review. The PI will report promptly any unanticipated problem (not expected, related, and provides a risk to the participant) to the IRB and to the sponsor. The PI will also report promptly any serious adverse event that is related to the spray intake (that occurred on site visits of CRN unit) to the IRB and the sponsor. The PI will also report to the IRB periodically if any serious adverse event not related to the spray but during the period of the study that occurred off site Emory or before spray intake or after the participant left the hospital and between study visits (please see the definition below of unrelated events). The PI prefers to report promptly any unrelated or related serious adverse events to the IRB and to the sponsor with a precision of relatedness to avoid any problems or misunderstanding. The PI will also report serious adverse events to the sponsor ([name]). The serious adverse events include: death, life threatening experience, hospitalization, disability or permanent damage, medical or surgical intervention, emergency seizures.

Written IND safety reports will be submitted to the FDA by the IND sponsor, for serious, unexpected suspected adverse reactions within 15 calendar days of learning of its occurrence. If the event is fatal or is deemed to be life threatening, the report will be made within 7 calendar days. The IND sponsor will also make an assessment of whether the event constitutes an unanticipated problem posing risks to subjects or others (UP). This assessment will be provided to the Emory University IRB, which, in turn will make a final

determination. If the Emory IRB determines an event is a UP it will notify the appropriate regulatory agencies and institutional officials.

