**Unrelated events:** If an event happened while the subject is coming to the first visit (before spray intake) or after the subject left the hospital (after spray but not at visit sites) or in between the 4 visits (not at visit sites) and that the subject told the experimenter about it, the event will be considered as an unexpected adverse event but unrelated to the treatment. Some patients might have comorbid anxiety traits or hyperactivity traits or being on drugs (other than oxytocin) and so sometimes these symptoms could underlie the medical baseline condition and are considered not related.

Expected Adverse events (please see the list above)	Unanticipated Problems (related, unexpected and risk to subjects)	Protocol deviations and non-compliance	Serious adverse events (deaths) related and unrelated
Reportable to IRB during continuing review board	Promptly reportable to IRB and DSMB	Promptly reportable to IRB	Promptly reportable to IRB and DSMB with specificity of relatedness
Reported to the sponsor at regular intervals	Promptly reportable to the sponsor	Reported to the sponsor at regular intervals	Promptly reportable to the sponsor
Not reportable to the FDA	Not reportable to the FDA, if not serious	Not reportable to the FDA	Promptly reportable to the FDA by the sponsor

Table 5.

Reportable events for the IRB (regarding the clinical visits).

The sponsor does not require reporting above and beyond IRB requirements.

The PI will review the overall data safety periodically. The PI is actually actively involved in testing participants and will make sure that all adverse events are written down and logged into adverse events templates after testing. Every week, the PI will review the regulatory binder to make sure that all the adverse events and procedures are done accordingly to the protocol. If there is any deviation or any unexpected adverse event or serious adverse event, the PI will report promptly all that to the IRB. The PI will make sure to review the literature on intranasal oxytocin (single doses) periodically and search for any adverse events. If there is any addition in the literature that the PI heard about or read about, she will inform the IRB promptly.

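### The investigator's relatedness label depends on where an event happened, not on whether the spray could have caused it, and the 'unexpected' label for off-site events conflicts with the protocol's own expected list

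*Combined protocol and SAP*

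**What the plan says.** All of this is in the Data and Safety Monitoring Plan of the combined protocol and SAP.

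- **Relatedness.** The rule covers any event, including serious events and death. The investigator treats it as related only if it happened on site, during a clinical visit, after the spray. It "will not be considered related to the treatment once the subject leaves the hospital".
- **Unrelated events.** For an event on the way to the first visit, after leaving the hospital or between visits, "the event will be considered as an unexpected adverse event but unrelated to the treatment". The pre-clinical visit text has the same location rule for visit 1.
- **Meaning of unexpected.** The pre-clinical visit text says: "Unexpected adverse event is an adverse event that is not listed in the investigator brochure". Two further alternatives follow: not listed at the observed specificity or severity, or not consistent with the protocol's risk information.
- **Expected list.** The clinical visits text says "we have a list of expected adverse events that could be linked to oxytocin inhalation or placebo inhalation" and gives 14 items, including headaches, nausea, rashes and tiredness.
- **How off-site events come to light.** On arrival at visits 2 to 5 participants are asked "visit if there were any changes in their health".
- **Log and unanticipated problems.** "The PI will take note of all related expected adverse events (list above) in a log document", and this goes periodically to the sponsor and IRB. Prompt reporting applies to "any unanticipated problem (not expected, related, and provides a risk to the participant"; Table 5 repeats the requirement that the problem be related.
- **Unrelated serious events.** "The PI will also report to the IRB periodically if any serious adverse event not related to the spray" occurs. The next sentence gives the investigator's preference for prompt reporting, and Table 5 says prompt.

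**The concern.** Relatedness should express a judgement about cause. Here it records the participant's location. A rash that appears in the scanner suite and the same rash that appears on the journey home get opposite labels, although nothing about the drug or the symptom differs. The documents give no onset or duration data that would justify departure as the cut-off.

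The label also affects how the event is handled. It decides whether the event enters the log of related expected events and whether it can count, for the investigator, as an unanticipated problem. Under Table 5, serious events go to the IRB and DSMB with their relatedness specified, so a location-based label would travel with the report.

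In a crossover with placebo and three oxytocin doses about a week apart, an event reported on arrival at the next visit could be linked to the preceding spray if onset was recorded. The rule settles relatedness without that step.

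The second strand is consistency. If being off site makes an event unexpected, staff have two incompatible instructions for a symptom on the expected list.

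**Working it through.** The plan gives no figure to reproduce and no arithmetic applies. The check sets the provisions side by side.

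**1. Is there any causal step in the investigator's rule?** Relatedness requires three things: on site, during the visit, after the spray. None concerns mechanism, plausibility, onset or alternative cause. The only clinical consideration is under Unrelated events, where symptoms may be put down to comorbid traits or other drugs. That can only move an event towards unrelated. An off-site event can never be classed as related.

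**2. What follows for an off-site event?**
- The log named under Relatedness holds events that are both related and expected. An off-site event fails the first condition.
- An unanticipated problem must be not expected, related and a risk. An off-site event fails the second condition, whatever its nature.

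**3. Is the unexpected label consistent with the rest of the plan?**
- Against the expected list and Table 5: no. The list carries no location limit, and Table 5's expected column points back to it. The Unrelated events text has no exception for listed items.
- Against the brochure-based definition: only partly checkable. The definition is a set of alternatives, so absence from the brochure is enough to make an event unexpected. The clinical visits text says that only some of the listed items are in the brochure. The brochure is not among the documents, so the number of the 14 that conflict with this definition is unknown.

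**4. Worked example: a non-serious headache, which is on the list.**

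| | On site after spray | At home after spray |
|---|---|---|
| Relatedness | related | unrelated |
| Expectedness | expected (list) | expected (list, Table 5) or unexpected (Unrelated events) |
| Log of related expected events | yes | no |
| IRB route | continuing review | continuing review (Table 5, expected) or prompt (text after Table 5, any unexpected event) |

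The unexpected label leads to the stricter of the two routes, so the conflict is about which instruction applies. It does not show that information is lost.

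**5. Serious events judged unrelated.** Relatedness says periodic and then expresses a preference for prompt; Table 5 says prompt. The substance points to prompt, and the periodic sentence needs editing.

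**6. Does any planned result depend on the label?** The Statistical analysis section specifies no adverse-event comparison by relatedness, so no planned estimate or test changes.

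**The case against.** The strongest reply is that the rule binds only the investigator's label and that much else stands around it:

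- The text after Table 5 says that all adverse events are logged in templates, and it sends any unexpected event promptly to the IRB without requiring relatedness.
- Serious events are reported whether related or not, and Table 5 has the sponsor report them to the FDA.
- The sponsor makes a separate assessment of unanticipated problems, on which the IRB makes the final determination.
- The sponsor also files IND reports of suspected reactions, which implies a causal judgement. It meets the investigator monthly and is responsible for continuing safety evaluation.
- Clinical investigators and the DSMB review adverse events.

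All of this stands, and it rules out several stronger conclusions that a reader might draw:

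- *Off-site events go unreported.* The reporting routes above contradict this.
- *Nobody assesses causality.* The sponsor's duties are not tied to the location rule. What can be said is that none of these reviews is described as re-assessing the investigator's label.
- *All 14 listed symptoms contradict the definition of unexpected.* The brochure would be needed to show that.
- *The forms arrive pre-marked unrelated.* The documents do not describe the template fields.

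The lack of a scheduled contact after the last spray session is a follow-up question, separate from classification, and is not counted here.

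What the reply does not remove is that a rule followed as written can label a delayed reaction unrelated, and that the plan contradicts itself on listed symptoms at home.

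**Conclusion.** The point holds as misclassification by the investigator. Relatedness is fixed by location for every event, including death. An off-site event therefore cannot be a related event, a logged related expected event, or an unanticipated problem under the investigator's definition. Separately, the unqualified unexpected label conflicts with the 14-item list and with Table 5, which leaves two IRB routes for a listed, non-serious, off-site event. One sentence on unrelated serious events also disagrees with Table 5.

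The size in events cannot be given, because the documents contain no onset times or event counts. A reader might infer that the trial's dose comparisons are biased. The documents do not support that, since no planned analysis uses relatedness. The risk would arise only if a safety summary were later restricted to related events, because it would then omit every off-site event.

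The conclusion assumes that the rule is applied as written and that no unstated procedure revises the label. Given the other reporting routes, it should be fixed, but it does not threaten the trial's results.

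**What to change.** 1. Replace the location rule in the pre-clinical visit, Relatedness and Unrelated events texts with a case-by-case causality assessment by the investigator or study physician, for every event wherever it occurs.
2. Judge expectedness by the listing and the risk information, not by place.
3. Reconcile those texts, the expected list, Table 5 and the paragraph after it on four matters: related, unexpected, unanticipated problem, and prompt versus periodic reporting.
4. The Healthy subjects screening section says that testing of the ASD patients is complete. Re-assess the ASD events already logged under the new rule, and link each to its preceding spray session where onset was recorded. A descriptive table by preceding treatment (placebo, 8, 24, 48 IU) after unblinding is optional.
5. Use the revised wording for any participant still to be tested, since the plan applies these rules to healthy subjects too.

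The cost is protocol wording and some assessment work. Re-attribution will be incomplete where onset was not recorded, and off-site events that were never reported cannot be recovered.
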